8.2.6. Adverse Events

At each study visit, all AEs will be identified and documented as detailed in Section [10](#) of this protocol.

8.2.7. Abdominal Computed Tomography Scan

In case of pancreatitis or suspected pancreatitis, an abdominal computed tomography (CT) scan should be performed as soon as possible in order to clarify the diagnosis and enable assessment of severity of this condition. An MRI may be performed as an alternative to the CT scan.

8.2.8. Glomerular Filtration Rate Estimation

Significant changes in laquinimod exposure, in particular in terms of unbound drug fraction, are predicted in patients with moderate and severe renal impairment (see Section 3.3.1).

Consequently, GFR will be estimated at all visits to monitor renal function in the study in order to identify subjects with potentially impaired laquinimod clearance. Subjects with a confirmed GFR ≤ 60 mL/min/1.73 m² should stop study medication temporarily and the GFR assessment should be repeated. If the renal impairment is confirmed (GFR ≤ 60 mL/min/1.73 m²), the subject should stop study medication permanently (see Section 7.3.4.1.5).

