7.1. Study Period

This is a continuation of the LAQ/5062 study as a multinational, multicenter, randomized, double-blind, parallel group study, assessing the safety, tolerability and efficacy of two doses of laquinimod in subjects with RRMS, followed by an open-label phase of laquinimod 0.6 mg daily (LAQ/5063 OL).

Subjects will enter this randomized, two active arms study immediately after completion of the LAQ/5062 core study. The blinding in both, core study (LAQ/5062) and its extension, will be maintained. Subjects will enter the open-label phase after completion of the Termination visit of LAQ/5063 active double-blind phase (completion of the full 36 weeks or as requested by the Sponsor).

The study duration is 36 weeks of double blind treatment (Week 0 [baseline] to Week 36 [termination]) or until the Sponsor's request. The duration of the open-label phase is as long as the Sponsor continues the development of laquinimod 0.6 mg for RRMS.

Subjects will be evaluated at study sites at Baseline (Week 0 / Termination (Week 36) of Core Study LAQ/5062), at Weeks 4, 8, 12, 16, 24, and 36 (Termination visit of LAQ/5063 active double-blind phase (completion of the full 36 weeks or as requested by the Sponsor).

For the Study 5063 open label extension phase, the visits will be at monthly intervals for the first 3 months and at three months intervals for the period of 24 months. Upon completion of the 24 month treatment period visits will be performed at 6 months intervals thereafter, where, for the purpose of this study, a month is 30 days and a visit is defined as X months \pm 7 days.

During the open label phase subjects will be evaluated at study sites for the following scheduled visits:

Baseline (Month 0 / Termination visit of LAQ/5063 active double-blind phase [completion of the full 36 weeks or as requested by the Sponsor]), Month 1, Month 2, Month 3, Month 6, Month 9, Month 12, Month 15, Month 18, Month 21, Month 24, Month 30, Month 36, Month 42, Month 48, Month 54, Month 60 and every 6 months thereafter, until termination (as long as the Sponsor continues the development of laquinimod 0.6 mg for RRMS) or early discontinuation.

Subjects who discontinue treatment for any reason will continue follow-up according to scheduled visits.

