7.3.4.1.5. Renal Impairment

To avoid exposures to higher levels of laquinimod (see Section 3.3.1), a stopping rule related to renal impairment has been introduced. Subjects who develop renal disease associated with moderate or severe functional impairment, defined as glomerular filtration rate (GFR) ≤ 60 mL/min/1.73 m², while participating in the study should stop study medication temporarily and the GFR assessment should be repeated. If the renal impairment is confirmed (GFR ≤ 60 mL/min/1.73 m²), the subject should stop study medication permanently.

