7.3.6. Unscheduled Visit

An unscheduled visit may be performed at any time during the study as deemed necessary by the Investigator. The date and reason for an unscheduled visit will be recorded.

The reasons for the unscheduled visit may be:

- Appearance of a new AE or an AE follow-up
- Change in concomitant medications
- Possible relapse
- Relapse follow-up
- Laboratory follow-up
- IMP dispensing, accountability and/or replacement
- Subject compliance
- Other, specify

Should the visit be related to a relapse, this will be clearly indicated on the CRF and the Study Neurologist/Physician will carry out a complete neurological evaluation (FS/ AI/ EDSS) and 25 foot walk test.

Additional analyses may be performed by the investigator and stated in the source documentation.

Mandatory Unscheduled Visit Procedures

- Vital signs
- Evaluation of AEs
- Evaluation of a suspected relapse/follow-up
- Ascertain use of effective contraception

Optional Unscheduled Visit Procedures

- ECG
- Physical examination
- Neurological examination (by the Study Neurologist/Physician)
- Laboratory tests (including estimation of GFR)
- IMP accountability
- Subject compliance

- Review of concomitant medications
- For women of child bearing potential, serum or urine β -hCG test may be performed

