Pancreatic amylase will be measured at each study visit. Lipase will be tested in case of abnormal pancreatic amylase results and on all follow-up visits until normalization of pancreatic amylase level. In case of suspected pancreatitis, the subject should undergo a thorough clinical evaluation including an abdominal CT scan as soon as possible in order to clarify the diagnosis and enable assessment of severity of this condition. An MRI may be performed as an alternative to the CT scan.

5. Liver Impairment

Subjects who develop any chronic liver disease associated with liver functional impairment while participating in the study should stop study medication.

6. Renal Impairment

Subjects who develop renal disease associated with moderate or severe functional impairment, defined as glomerular filtration rate (GFR) ≤ 60 mL/min/1.73 m², while participating in the study should stop study medication temporarily and the GFR assessment should be repeated. If the renal impairment is confirmed (GFR ≤ 60 mL/min/1.73 m²), the subject should stop study medication permanently.

7. Management of pregnancy and pregnancy testing during the study

Exposure to laquinimod during pregnancy should be avoided.

To further emphasize the importance of use of effective contraception and avoidance of pregnancy under laquinimod exposure (see Section 3.4), and to reduce as much as possible the exposure to laquinimod if a pregnancy occurs despite all recommended measures, all subjects who are women of childbearing potential will be instructed about the teratogenicity and potential delayed risks for a child exposed in uterus to laquinimod. These subjects will also be counseled about the importance of using two acceptable methods of birth control throughout the entire treatment duration and until 30 days after the last dose of treatment was administered and about the need to stop treatment immediately if pregnancy is suspected.

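### Section 8.2.8 asks for a confirmed low GFR before the temporary stop; Section 7.3.4.1.5 and Appendix 10 do not, and no passage says which prevails

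*Combined protocol and SAP*

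**What the plan says.** Three places in the current text state the rule, all with a cut-off of GFR at or below 60 mL/min/1.73 m².

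- **Section 8.2.8** applies the temporary stop to "Subjects with a confirmed GFR" at or below the cut-off and asks for the GFR to be repeated. The permanent stop then depends on a second condition, "If the renal impairment is confirmed". The paragraph ends with a cross-reference to Section 7.3.4.1.5.
- **Section 7.3.4.1.5** opens "Subjects who develop renal disease associated with moderate or severe functional impairment, defined as glomerular filtration rate (GFR" and then gives the cut-off. Such subjects, "while participating in the study should stop study medication temporarily and the GFR assessment should be repeated". The stop becomes permanent if the repeat confirms the impairment.
- **Appendix 10, item 6**, matches Section 7.3.4.1.5: the subject "should stop study medication temporarily and the GFR assessment should be repeated", with the permanent stop on confirmation.

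On timing, Section 7.1 says that after Month 24 "visits will be performed at 6 months intervals thereafter, where, for the purpose of this study, a month is 30 days", with a window of ±7 days on each visit. Section 7.3.6 allows an unscheduled visit for laboratory follow-up and lists GFR estimation among the optional procedures there.

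**The concern.** A stopping rule has to give every site the same instruction. Here a site working from the assessment section could keep a subject on drug after one low GFR until a second test confirms it. A site working from the stopping-rule section or the appendix would stop first and repeat afterwards. The number of low values needed for the permanent stop differs in the same way.

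Section 7.3.4.1.5 gives the purpose of the rule as avoiding raised laquinimod exposure. Section 3.4.1.7 lists organ-impairment stopping rules among the measures added after the serious cardiovascular events seen at 1.2 and 1.5 mg in other studies. If the passages disagree on when dosing stops, that purpose is met differently from site to site.

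**Working it through.** The protocol states no figure to reproduce for this point. The check is a comparison of the three passages, followed by simple arithmetic on visit timing.

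**Step 1: the passages side by side**

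| | Section 8.2.8 | Section 7.3.4.1.5 | Appendix 10, item 6 |
|---|---|---|---|
| Cut-off (mL/min/1.73 m²) | ≤60 | ≤60 | ≤60 |
| Renal disease named in the trigger | No | Yes | Yes |
| Confirmation before temporary stop | Yes | No | No |
| Repeat after temporary stop | Yes | Yes | Yes |
| Confirmation before permanent stop | Yes | Yes | Yes |
| Time set for the repeat | None | None | None |

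**Step 2: what 'confirmed' means.** No passage defines it for GFR. The liver guidance in Appendix 10 (item 1.1) uses confirmation to mean a repeat test, and says explicitly when none is needed before the drug is stopped. On that usage a confirmed value is one low result plus one low repeat, so two values.

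**Step 3: number of low values needed, read literally**

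- Section 7.3.4.1.5 and Appendix 10: temporary stop after 1; permanent stop after 1 + 1 = 2.
- Section 8.2.8: temporary stop after 2; permanent stop after 2 + 1 = 3.

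**Step 4: the trigger.** In Section 7.3.4.1.5 and Appendix 10 the cut-off defines the functional impairment, but the sentence also names renal disease.

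- If the cut-off alone is the trigger, there is no second difference from Section 8.2.8.
- If renal disease is a further requirement, those two passages are narrower than Section 8.2.8. An isolated low GFR would then fall only under Section 8.2.8.

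The text does not settle which is meant. The counts of 1 and 2 in Step 3 assume that the low GFR meets the trigger.

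**Step 5: possible extra time on drug under the literal reading of Section 8.2.8**

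- Lower end: an unscheduled laboratory visit, so a matter of days.
- Upper end, assuming that the second GFR waits for the next scheduled visit after Month 24: 6 × 30 = 180 days nominal. Each visit may move by 7 days, so the interval runs from 180 − 14 = 166 to 180 + 14 = 194 days.

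**Step 6: the exposure the rule guards against (Section 3.3.1).** Observed exposure in moderate renal impairment rose 1.4-fold. The physiologically based model predicts unbound exposure of 1.65-fold (moderate) and 1.86-fold (severe) with multiple 0.6 mg doses.

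**The case against.** The strongest reply is that this is a one-word slip and not two rules. The cut-off and the order of stop, repeat and permanent stop are the same in all three places. In Section 8.2.8 the word comes before the repeat that would do the confirming, so the sentence makes little sense unless the word is ignored, and the paragraph sends the reader to Section 7.3.4.1.5. Much of this stands: a slip is a plausible explanation. But the word is part of an operative instruction in the section that governs GFR measurement. The liver guidance gives it a definite meaning, and the cross-reference does not say that the other section prevails.

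Three stronger readings are tempting, and the documents do not support them.

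- **That subjects will stay on drug for about six months.** That is only the upper case. Section 7.3.4 asks for clinically significant laboratory changes to be repeated and followed up, and Section 7.3.6 provides a visit for it. The absence of a time for the repeat is common to all three passages, so it is not part of the contradiction.
- **That the delay takes a subject close to the discontinued 1.2 mg dose.** Multiplying the model's unbound ratios by dose gives 0.6 × 1.65 = 0.99 mg and 0.6 × 1.86 = 1.12 mg. The observed ratio gives 0.6 × 1.4 = 0.84 mg. Section 3.3.1 calls the predicted increase in moderate impairment modest, and 0.99 mg is 17.5% below 1.2 mg. Only the severe-impairment prediction comes near. The figures show why the rule was written; they do not measure a risk from the wording.
- **That Section 7.3.4.1.5 always stops drug at the first low value.** It does not say so. If renal disease is a separate requirement, one low value without it would not trigger the stop there, so it cannot be claimed that this section adds no time on drug.

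**Conclusion.** The inconsistency is real and sits in current text. Section 8.2.8 requires a confirmed low GFR before the temporary stop, and the other two passages do not. Its literal count is two and three low values against one and two, and it is circular within itself. The reference to renal disease in the other two passages leaves the trigger ambiguous; it is not a proven second contradiction.

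The consequence is that sites may differ on whether dosing continues during confirmation, by anything from days to about 166–194 days. The upper range assumes that the repeat waits for the next six-monthly visit. The count assumes that confirmation means a repeat test, as in the liver guidance, and that the low GFR meets the trigger. The documents give no rate of low GFR, so the number of subjects affected cannot be estimated.

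This should be corrected because it is a safety stopping rule and the correction is cheap. Nothing here bears on which of the passages is clinically right.

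**What to change.** Reconcile Section 8.2.8, Section 7.3.4.1.5 and Appendix 10, item 6, so that all three state the same trigger (including whether renal disease is required in addition to the GFR value), the same sequence, and the same number of qualifying values for the temporary and the permanent stop. The sponsor's medical team should decide the clinical content. Notify sites of the agreed text.

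The cost is wording in up to three places and a site notice. Aligning the text does not by itself add a visit or a test; whether the agreed content does is for the medical team to settle.

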8.2.9. Cardiovascular Risk Assessment and Management

Evaluation and management of major modifiable cardiac risk factors (eg, diabetes, high blood pressure, hyperlipidemia, tobacco smoking) will be performed at the time points indicated in Table 7. In addition, an evaluation should take place as soon as possible for subjects already in the study, following approval of Amendment #10.

Cardiovascular risk management should be conducted according to evidence-based, local standard-of-care procedures. Subjects will undergo referral to a suitable clinic if needed.

8.3. Assessment of Subject Compliance

At each study visit, the Investigator, Site Coordinator and/or pharmacist will assess the subject's compliance with the study requirements. This will include checks of protocol compliance and use of laquinimod.

The subject will return all unused tablets and/or capsules (following the switch to capsules) in their original packages, blisters/bottles and all used partially empty and empty blisters/bottles and unused IMP at each visit to the study. Compliance with the dosing regimen will be determined by performing IMP accountability of returned blisters/bottles of the IMP used and unused. The number of unused tablets/capsules will be recorded on the CRF by site personnel. Percent compliance will be calculated as the number of used tablets/capsules divided by the number of total tablets/capsules expected to be used, multiplied by 100.

Subjects with less than 75% overall compliance during the entire study will be considered non-compliant, although they will continue to be followed-up and included in the intent-to-treat (ITT) cohort. Subjects who fail to comply with the study requirements may be withdrawn from the study, following consultation with the Sponsor.

8.4. Ancillary Studies

The Ancillary studies are relevant for LAQ/5063 active double-blind phase only.

8.4.1. Pharmacokinetic Sub-Study

Blood samples for PK evaluation will be performed in a sub-set of countries and sites.

For PK evaluation blood sample (2 mL/each) will be collected from subjects at one time point prior to first administration of the IMP (one day after randomization into LAQ/5063), and on Week 36 at the following time points: pre-dose and at 10, 30, 45, 90 minutes, 3, 6, 24 hours and 72 hours (day 3 post-study termination), 144 hours (day 6 post-study termination), 240 hours (day 10 post-study termination) and at 336 hours (day 14 post-study termination). The blood samples will be collected into tubes containing sodium heparin. All participants in this study should administer the IMP dose at the same time in the morning.

8.4.2. Population Pharmacokinetic (PPK) Study

Blood samples for PPK study will be collected in all study sites. Subjects participating in PPK study are not necessarily participating in PK sub-study.

For PPK evaluation, 1 blood sample (2 mL/each) will be collected from subjects Week 36/Early Termination. The date and time of the blood sample, as well as the date and time of the last dose prior to the sample will be recorded on the CRF. A review of the treatment compliance will include information on the last week compliance regarding tablets intake. The blood samples will be collected into tubes containing sodium heparin.

8.4.3. Samples Handling for PK and PPK studies

Plasma will be separated by centrifugation at nominally +4°C. Deviations from the blood sampling times will be recorded in the appropriate CRFs. Samples will be prepared by the site and sent frozen to the central laboratory for storage at -70°C. Samples for PK evaluation will be sent periodically to an analytical facility for analysis. The analytical facility is:

Teva Pharmaceutical Works Co. Ltd.
Innovative R&D
Bioanalytical Laboratory
[name]
Debrecen
4042 Hungary

8.4.4. Bioanalysis

The concentrations of laquinimod will be determined in blood plasma using LC-MS/MS (Liquid Chromatography Tandem Mass Spectrometry) in accordance with the ABR-method M-0085A. Quantitation will be based on an internal standard, a stable isotope of laquinimod containing six ¹³C atoms. The plasma will be prepared for injection onto the LC-MS/MS system by protein precipitation.

8.4.5. Pharmacokinetic Calculation

For calculation of the PK parameters, WinNonlin professional will be used. The PK parameters for each individual will be determined. The maximum plasma concentration (C_{max}) and the time to maximum plasma concentration (t_{max}) values will be determined from the observed plasma concentration-time curve as the maximum concentration and the corresponding time after each sampling period. The elimination rate constant (λ) at steady rate will be estimated by linear regression analysis of the terminal slope of the logarithmic plasma concentration-time curve. The area under the plasma concentration-time curve will be calculated by using the linear/logarithmic trapezoidal rule. Time dependency will be evaluated by fitting a compartmental model to the data for each subject. An additional analysis will be performed by fitting a population model to the data and possible time, dose and sex dependencies will be investigated.

9. INVESTIGATIONAL MEDICINAL PRODUCT

9.1. Description

Laquinimod 0.3 mg tablets and/or matching placebo tablets will be administered to the subjects.

Laquinimod 0.3 mg tablets are white to off-white round biconvex tablets.

The active tablets contain laquinimod sodium salt equivalent to 0.3 mg laquinimod. All inactive ingredients (excipients) are pharmaceutically acceptable. Matching placebo tablets contain no active ingredients. The matching placebo tablets will be identical in color and appearance to the tablets containing 0.3 mg of laquinimod.

Study drugs will be supplied to the study sites by Teva Pharmaceutical Industries, Ltd., through a distribution center.

The placebo paragraph is relevant for LAQ/5063 active double-blind phase only.

Upon approval of the Global Amendment # 4 to Protocol LAQ/5063 the IMP were switched from laquinimod tablets 0.3 mg, administered as two tablets once daily, to laquinimod capsules 0.6 mg. The clinical dosage remains unchanged at 0.6 mg of laquinimod, administered orally once a day.

9.2. Assignment of Treatment

At baseline (termination visit of core study), after meeting the inclusion/exclusion criteria, assignment of a subject to a treatment group will be performed by the Interactive Voice Response system (IVRS) according to the randomization scheme produced by Teva Global BioStatistics and Global BioMedical Informatics units. The subject number remains as in the core study.

The assignment of treatment is relevant for LAQ/5063 active double-blind phase only.

9.3. Investigational Medicinal Product Manufacturing

Siegfried Ltd., is the manufacturer of laquinimod tablets. Manufacturing was carried out in accordance with GMP applicable to IMPs.

The new study drug, laquinimod capsules 0.6 mg, which will be introduced during the open label phase of LAQ/5063 OL upon approval of Amendment # 4, is manufactured in compliance with current GMP standards by Teva Pharmaceutical Industries Ltd. Israel.

9.4. Packaging And Labeling

Laquinimod 0.3 mg tablets and their matching placebo will be packaged into PVC-PVDC blisters. The blisters will be packed into monthly packs which will be assigned to subjects by using an IVRS.

The CSU at Teva Pharmaceutical Industries, Ltd., Israel, will be responsible for secondary packaging, labeling and distributing of study drugs, according to EU regulations. These activities will be carried out by a sub-contracted company (Clinical Research Organization [CRO]).

Study drugs will be packed and labeled in a way that meets the regulatory requirements and maintains the blinded nature of the study.

The label of the monthly pack will include fixed information section to include for example the product name, storage conditions, instructions etc...) and variable information section. The variable information section will include 3 parts: one detachable part, which will be attached to the source document upon pack dispensing, 1 part will be attached to the prescription form (where applicable) and 1 part to remain on the pack. The variable information section will include the following variable data: batch code, pack number, and expiration date (all to be pre-printed) and blank fields for investigator name, visit number and subject number. These blank fields will be manually filled-in by the Investigator upon provision of pack to the subject.

At each scheduled visit (except for termination visit), the subject will receive one or more monthly pack/s (according to visit duration). The amount of study drugs dispensed will suffice until the following dispensing visit.

The placebo, IVRS and blinding paragraphs are relevant for LAQ/5063 active double-blind phase only. For the open-label phase (LAQ/5063 OL) a batch number will be allocated instead of a batch code number.

The replacement of the current drug supply, laquinimod tablets 0.3 mg, with laquinimod capsules 0.6 mg during the open label phase of LAQ/5063 OL, the process of packaging and labeling will be changed to the following:

The study drugs will be packaged in round 50 cc white high density polyethylene bottles containing 35 capsules. The bottles are capped with child-resistant polypropylene caps, each equipped with a silica desiccant insert.

The primary packaging is performed at a Teva Pharmaceutical Industries Ltd. plant. The secondary packaging and labeling for subjects is performed under the responsibility of the Clinical Supply Unit of Teva Pharmaceutical Industries Ltd, according to European Union (EU) regulations and International Conference on Harmonization (ICH) guidelines as adopted by the FDA – Good Clinical Practice (GCP) (E6).

Each bottle will be identified by a unique bottle number that will be defined by sequential lists produced by Teva.

The label on the bottles will include a fixed information section (to include the product name, storage conditions, instructions etc.) and variable information section. The variable information section will include 3 parts: 2 detachable parts, which will be attached to the subject's file upon bottle dispensing and 1 part to remain on the bottle. The variable information section will include the following variable data: batch number, bottle number, and expiration date (all to be pre-printed) and blank fields for investigator name, visit number and **subject number**. These blank fields will be manually filled-in by the Investigator upon provision of bottle to the subject.

